Observational multicenter study

Number/code

Version 3.0

Date March 2018

Registry of COPD patients who undergo outpatient treatment or are under surveillance at outpatient polyclinic healthcare institutions of the Russian Federation in Moscow

PROTOCOL SYNOPSIS

Registry of COPD patients who undergo outpatient treatment or are under surveillance at outpatient polyclinic healthcare institutions of the Russian Federation in Moscow

Principal investigator:

[name], Doctor of Medicine, Professor, Head of laboratory, FSI «SRI of Pulmonology» of FMBA of Russia.

Sites, number of participants

At least (2000) patients at approximately 15 polyclinic sites in Moscow.

Investigators: pulmonologists of outpatient polyclinic care in Moscow

It is planned to enrol approximately 120 patients with diagnosed COPD **at each of approximately 15 polyclinic institutions of Moscow** (in total at least 2000 patients)

Study period

Planned study timeframes

Planned timeline for enrolment of first patient	Fourth quarter 2016
Planned timeline for enrolment of last patient	Second quarter 2018
Planned timeline for last patient out	Third quarter 2018
Planned timeline for database lock	Fourth quarter 2018
Planned timeline for final report preparation	First quarter 2019
Planned timeline for publication of results	Third quarter 2019

Medicinal product (name, dose, administration route) and concomitant therapy

Not applicable.

Background

Experts of the World Health Organization (WHO) estimated that approximately 210 mln. people worldwide suffer from COPD. In our modern age, COPD represents one of the leading

chronic diseases alongside with arterial hypertension, coronary heart disease and diabetes mellitus. They account for more than 30% among other human pathologies. COPD ranks fourth among causes of death worldwide, and is assumed to ascend to the third place by 2020. According to estimations using epidemiological markers, in the Russian Federation there are approximately 11 mln. people suffering from COPD. Whereas according to official statistics their total number in the Russian Federation amounts to only 2.4 mln. This is due to underdiagnosis and patients seeking medical attention too late, which result in detection of the disease at advanced stages when even the most modern treatment methods cannot delay steady progression of the disease. [1]

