The registry will include all patients with registered diagnoses J40 - J44 according to ICD-10 with spirometry results confirming COPD diagnosis, who are at the study start under outpatient surveillance, and also newly registered patients diagnosed with COPD (ICD-10 J40 - J44, as confirmed by spirometry results) during the conduction of the registry program at the selected polyclinic institutions of Moscow (according to ICD: J40 - Bronchitis, not specified as acute or chronic, J41 - Simple and mucopurulent chronic bronchitis, J41.0 - Simple chronic bronchitis, J41.8 - Mixed simple and mucopurulent chronic bronchitis, J 42 - Unspecified chronic bronchitis, J 43 - Emphysema, J 44 - Other chronic obstructive pulmonary disease) based on regular (yearly) retrospective analysis of patient records with data entry into a consolidated database.

It is planned to enrol into the study approximately **2000** male and female patients over 40 years of age with diagnosed COPD (as confirmed by spirometry results).

The present observational multicenter descriptive study will be conducted in the setting of routine clinical practice of outpatient polyclinic institutions. There is no hypothesis to be tested in this study.

The study will be conducted in outpatient polyclinic institutions of the primary medical care system of Moscow. Pulmonologists of the primary medical care system will be engaged as investigators. These are the physicians, whom the patients with tentative COPD diagnosis are referred to in the Russian Federation and who within the scope of their responsibilities have access to source medical records and who evaluate the quality of diagnosis and extent of treatment prescribed to COPD patients.

The present study is observational therefore it does not require a treatment regimen or directions for patient management. The patients receive medical care in line with routine practice for treatment of this disease in the Russian Federation. Patient participation in the study should not in any way affect the principles and extent of treatment received by the patient according to routine clinical practice.

Physicians-investigators will enter into the study the information (data) concerning COPD patients, both those already registered at the selected medical treatment and preventive care institution, and newly registered patients as they seek attention at the outpatient polyclinic institutions.

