3. STUDY PLAN AND PROCEDURES

The registry of COPD patients represents a non-interventional multicenter descriptive retrospective study of all COPD patients, which medical records will be retrospectively added to the registry database and newly diagnosed under outpatient surveillance at the selected polyclinic institutions of Moscow with retrospective entry of data.

it will include all patients with registered diagnoses J40 - J44 according to ICD-10 with spirometry results confirming COPD diagnosis, who are at the study start under outpatient surveillance, and also newly registered patients diagnosed with COPD (ICD-10 J40 - J44, as confirmed by spirometry results) during the conduction of the registry program at the selected polyclinic institutions of Moscow (according to ICD: J40 - Bronchitis, not specified as acute or chronic, J41 - Simple and mucopurulent chronic bronchitis, J41.0 - Simple chronic bronchitis, J41.8 - Mixed simple and mucopurulent chronic bronchitis, J 42 - Unspecified chronic bronchitis, J 43 - Emphysema, J 44 - Other chronic obstructive pulmonary disease) based on regular (yearly) retrospective analysis of patient records with data entry into a consolidated database.

It is planned to enrol into the study approximately **2000** male and female patients over 40 years of age with diagnosed COPD (as confirmed by spirometry results).

The present observational multicenter descriptive study will be conducted in the setting of routine clinical practice of outpatient polyclinic institutions. There is no hypothesis to be tested in this study.

The study will be conducted in outpatient polyclinic institutions of the primary medical care system of Moscow. Pulmonologists of the primary medical care system will be engaged as investigators. These are the physicians, whom the patients with tentative COPD diagnosis are referred to in the Russian Federation and who within the scope of their responsibilities have access to source medical records and who evaluate the quality of diagnosis and extent of treatment prescribed to COPD patients.

The present study is observational therefore it does not require a treatment regimen or directions for patient management. The patients receive medical care in line with routine practice for treatment of this disease in the Russian Federation. Patient participation in the

study should not in any way affect the principles and extent of treatment received by the patient according to routine clinical practice.

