Physicians-investigators will enter into the study the information (data) concerning COPD patients, both those already registered at the selected medical treatment and preventive care institution, and newly registered patients as they seek attention at the outpatient polyclinic institutions during the registry conduction period.

The main purpose of the present study consists in collection of data concerning COPD patients under surveillance at outpatient polyclinic institutions of Moscow using patient medical records and their medical history. This protocol does not specify any obligatory visits or examinations.

Patient data will be entered into the registry de-identified. The patients will be identified by their screening number and initials. Then the Physician-investigator will evaluate patient compliance with inclusion criteria. The study will enrol patients meeting all the inclusion criteria and not having any of the exclusion criteria.

Only the physician who enters patient data into the regional COPD registry possesses patient contact information, and henceforth only this physician will enter de-identified patient data according to study design. This physician does not influence the choice of examination extent, treatment strategy and medication.

Visit "Enrolment". At this visit de-identified data of the patients will be included into the study. De-identified data are entered retrospectively based on analysis of the outpatient medical records.

At this visit the Physician-investigator will complete the following information (collected retrospectively):

1. Verify inclusion/ exclusion criteria
2. Establish the date of COPD diagnosis
3. Collect medical history concerning significant comorbidities and clinical characteristics, rate of exacerbations, pneumonia cases, hospitalizations, number of outpatient visits concerning COPD, number of days of disability in the year prior to enrolment
4. Evaluate smoking status. Wherever possible, smoking in pack-years
5. Collect medical history concerning treatment regimens, including different regimens of CS use, which the patient took/was prescribed in the year prior to enrolment into the registry (trade name of the medicinal product and INN, doses, dosing regimen, duration of use)
6. Collect demographic data and information concerning the patient's socioeconomic status

Number/Code:
Version:
Date:

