4. PATIENT POPULATION

4.1 Physicians-investigators

The present study is non-interventional (an observational, multicenter, descriptive study). Randomly selected polyclinic institutions of Moscow will take part in the study and enrol into the registry 2000 COPD patients.

The patient population includes male and female patients over 40 years of age, smokers or ex-smokers, under outpatient surveillance at polyclinic institutions of Moscow with diagnosis codes according to ICD J40 - J44 and diagnosed COPD, as confirmed by spirometry results.

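### The plan promises entry of every eligible patient yet also sets enrolment targets, and it has no rule for choosing or counting records where a site holds more patients than it enters

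*Combined protocol and SAP*

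**What the plan says.** Two kinds of statement describe who enters the registry.

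- **Everyone eligible.** Synopsis, Study design: "The registry will include all patients with registered diagnoses J40 - J44 according to ICD-10 with spirometry results confirming COPD diagnosis". Section 3 says the same: "it will include all patients with registered diagnoses J40 - J44 according to ICD-10 with spirometry results confirming COPD diagnosis". Both extend this to patients newly registered while the registry runs.
- **A planned number.** Synopsis, Sites, number of participants: "At least (2000) patients at approximately 15 polyclinic sites in Moscow". For each site: "It is planned to enrol approximately 120 patients with diagnosed COPD". Section 3 gives the total as a round figure ("It is planned to enrol into the study approximately" 2000), and Section 4.1 gives it as 2000 outright.

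On selection, Section 4.1 says: "Randomly selected polyclinic institutions of Moscow will take part in the study and enrol into the registry 2000 COPD patients". Chance therefore operates between sites. For patients, Section 3 gives eligibility only: "The study will enrol patients meeting all the inclusion criteria and not having any of the exclusion criteria". New cases are entered on presentation: "newly registered patients as they seek attention at the outpatient polyclinic institutions during the registry conduction period". Patients already registered are entered retrospectively from outpatient records, and no visit is obligatory (Sections 3 and 7.1).

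Section 12.5 says that no sample size was calculated, so the figure of 120 has no stated basis. Section 12.4 plans descriptive statistics only. The synopsis adds 95% confidence intervals for percentages where appropriate.

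**The concern.** A full census needs no planned number per site, and a planned number below the eligible total needs a rule for who is left out. The plan has the census statement and the numbers but not the rule.

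The study tests no hypothesis, so the description is the whole result and depends on who was entered. The primary profile includes severity grade, phenotype and exacerbation rate. The secondary endpoints include exacerbations, hospitalizations, outpatient visits, temporary disability and treatment. All of these could plausibly vary with how often a patient attends. The synopsis also expects the phenotype percentages and treatment findings to be used beyond Moscow.

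A confidence interval reflects sampling variation around whatever mix of patients was entered. It does not reveal that the mix was selected.

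**Working it through.** **1. The enrolment figures.** Inputs are from the synopsis.

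- Sites × patients per site = 15 × 120 = 1800. This is 200 (10%) below the stated minimum of 2000.
- Reaching 2000 needs 2000/15 = 133.3 patients per site, or 2000/120 = 16.7 sites.
- Because both inputs are approximate, small changes close the gap: 17 × 120 = 2040, or 15 × 134 = 2010.

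The shortfall is a matter for reconciliation. It also shows that 120 cannot be read as an exact count of eligible patients.

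**2. Is there a selection rule?** Synopsis (Study design) and Sections 3, 4.1, 4.2 and 7.1 were read together. They give random choice of sites, eligibility criteria and a list of data items. They give no consecutive, random or list-based rule for records and no instruction for a site with more eligible patients than it will enter. A screening number is mentioned, but no tally of patients listed, eligible and entered. No section gives the eligible number at any site.

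**3. Hypothetical size, visit rate (a secondary item).** None of these inputs is in the documents. Let visit rates be gamma-distributed with coefficient of variation CV. Let a patient with rate λ be entered by time t with probability 1 − exp(−λt), and let f be the fraction of eligible patients entered. Then

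mean rate among entered / true mean = [1 − (1 − f)^(1 + CV²)] / f.

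The ratio does not depend on the mean itself.

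| f | CV 0.6 | CV 1.0 |
|---|---|---|
| 30% | (1 − 0.7^1.36)/0.3 = 1.28 | (1 − 0.7²)/0.3 = 1.70 |
| 50% | (1 − 0.5^1.36)/0.5 = 1.22 | (1 − 0.5²)/0.5 = 1.50 |
| 100% | 1.00 | 1.00 |

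Visit rate drives selection in this model, so it shows the full effect. Any other item is affected only through its association with attendance.

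**4. Hypothetical size, a primary item.** Take the frequent-exacerbator share, again with assumed inputs: true share p = 25%, attendance RR times that of other patients, and a site with M eligible patients that enters the first 120 to attend. Solve M[p(1 − e^(−RR·t)) + (1 − p)(1 − e^(−t))] = 120 for t. The expected share is then M·p(1 − e^(−RR·t))/120.

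- For RR = 2 and M = 200, put x = e^(−t). Then x² + 3x − 1.6 = 0, so x = 0.462, and the share is 200 × 0.25 × (1 − 0.2136)/120 = 32.8%.
- For RR = 2 and M = 133, 300 and 600: 27.3%, 35.6% and 37.9%.
- For M = 200 and RR = 1.5 and 3: 29.6% and 36.7%.
- For RR = 1, or M of 120 or less: 25.0%, no bias.

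For comparison, the 95% half-width at n = 2000 and p = 25%, treating patients as independent, is 1.96 × √(0.25 × 0.75/2000) = 1.9 points. A bias of this kind could exceed the interval without being visible in it.

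**The case against.** The strongest reply is that the plan is coherent if read as entering everyone eligible, with about 2000 expected. The per-site figure is approximate, the total is a minimum, and nothing tells a site to stop at 120. This largely stands. A reader might infer a hard quota, but the text states none. It follows that the documents also do not support a claim that equal site quotas turn the pooled result into an average over polyclinics. What remains is that the plan does not say sites continue until every eligible patient is entered, and Section 4.1 gives a flat total of 2000.

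A reader might also infer that investigators may pick whichever records they like. The documents do not say so; their stated instruction is to include all. Discretion would arise only by default, where a site enters fewer than it holds.

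The attendance mechanism is the weakest link. Entry on presentation is stated for newly registered patients, for whom repeat attendance matters less. Already registered patients come from record review, whose order is not stated and could be unrelated to attendance. In addition, one secondary objective concerns patients who seek attention, so for that objective attenders are partly the target.

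Finally, data come from retained records, so omitted patients could still be added before database lock. That makes the problem easier to correct, provided someone counts who was omitted.

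**Conclusion.** The point holds as an unreconciled conflict between a census statement and enrolment targets, with no rule or count for patients left out. Following the plan as written can yield a convenience sample for a purely descriptive primary objective. This goes beyond missing detail, because a concrete and inexpensive method would reduce the risk.

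Two stronger conclusions are tempting but not supported. The first is that the profile is skewed to frequent attenders. That direction is plausible but not established, because the order of record review is unknown. The second is that 22% to 70% estimates the bias in the primary profile. Those figures concern visit rate and rest on an assumed distribution, assumed fractions entered and strict attendance order over the whole sample. The frequent-exacerbator figures are equally hypothetical. Zero bias is also within range: it follows from full entry, and equally from any selection unrelated to attendance.

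The change should be made. Confidence is medium, because eligible numbers per site are not given.

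**What to change.** In Sections 3 and 4.1, with the synopsis aligned:

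1. Reconcile the census statement with the figures of 120, 15 and 2000, and say whether each site enters every eligible patient.
2. Have each site make a dated list of its registered J40–J44 patients. It then enters every eligible one or, if it will enter fewer, takes a random or every k-th draw from the list regardless of attendance.
3. Flag newly registered cases separately.
4. Record per site the numbers listed, eligible and entered. If sampling fractions differ between sites, report an estimate weighted by number eligible beside the unweighted one. Weighting corrects for unequal fractions between sites; it does not correct for who was chosen within a site.
5. Version 3.0 is dated March 2018 and last enrolment is planned for the second quarter of 2018, so some sites may have finished. There, record the number listed and compare entered with not-entered patients on age, sex and ICD code. This can reveal a gross difference but cannot exclude selection by attendance.

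The cost is modest extra record work at sites, including eligibility checks on some records that are not entered, and slightly wider weighted intervals. A draw from the list needs no additional patients.

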Appendix 1 – Classification of COPD severity (criteria)

APPENDIX 2. FEDERAL CLINICAL GUIDELINES FOR DIAGNOSIS AND TREATMENT OF CHRONIC OBSTRUCTIVE PULMONARY DISEASE 2014 LIST OF ABBREVIATIONS

List of abbreviations	Definition of the terms
AE	Adverse event
ADR	Adverse drug reaction
CRF	Case report form (paper)
EC	Ethics Committee
GCP	Good clinical practice
ICH	International Conference on Harmonization
IEC	Independent Ethics Committee
NIS	Non-interventional study
PI	Principal investigator
Variables	Parameters, patient examination results which can change in the course of time

1. INTRODUCTION

1.1 Background

Definition of COPD

COPD is a preventable and treatable disease characterized by persisting airflow limitation which typically progresses and associated with marked chronic inflammatory response in the lungs to pathogen particles or gases. In a number of patients, exacerbations and comorbidities can affect the general severity of COPD (GOLD 2015).

COPD diagnosis should be suspected in all patients with dyspnoea, chronic cough or expectoration and/or history of risk factors characteristic of this disease.

Experts of the World Health Organization (WHO) estimated that approximately 210 mln. people worldwide suffer from COPD. In our modern age, COPD represents one of the leading chronic diseases alongside with arterial hypertension, coronary heart disease and diabetes mellitus. They account for more than 30% among other human pathologies. COPD ranks fourth among causes of death worldwide, and is assumed to ascend to the third place by 2020. According to estimations using epidemiological markers, in the Russian Federation there are approximately 11 mln. people suffering from COPD. Whereas according to official statistics their total number in the Russian Federation amounts to only 2.4 mln. This is due to underdiagnosis and patients seeking medical attention too late, which result in detection of the disease at advanced stages when even the most modern treatment methods cannot delay steady progression of the disease. [1]

In the Russian Federation, diagnosis and treatment of COPD patients is performed primarily at community-based primary care outpatient polyclinic institutions. Every year in the Russian Federation there are approximately 100 thousands new cases of the disease diagnosed (statistics digest "Morbidity rates in adult population of Russia in 2012"). However, as a rule, COPD is diagnosed at advanced stages when complaints become a major problem for the patient. In many regions of the country, spirometric testing have still not been introduced into routine practice of primary care physicians, although on the positive side, in the recent years facilities of primary care outpatient polyclinic institutions have improved substantially.

In the recent years, several studies with an objective to ascertain the real prevalence of COPD have been conducted in Russia. These studies demonstrated that COPD was observed approximately in 8% of the population over 18 years of age (Postnikova L.B., et al. Pulmonology, 2011) [3], and among those over 18 years of age the prevalence of this disease touches on 14.5% [4], (Zhestkov A.V., et al. Pulmonology, 2009).

In 2012 there were 2.7 mln. of COPD patients under surveillance at outpatient polyclinic institutions in the Russian Federation. However, we do not have at our disposal updated information regarding the prevalence of the disease in specific cities, distribution of these COPD patients by extent of airway obstruction. Data on pharmacotherapy are only approximate.

In developed countries, total economy expenses associated with COPD take 2nd place in the structure of pulmonary diseases after lung cancer, and if we consider direct expenses COPD takes the 1st place exceeding direct expenses for bronchial asthma 1.9-fold. Economy expenses per patient associated with COPD 3 times exceed those for an asthma patient. Scarce reports of direct medical expenses in COPD show that more than 80% of resources are spent on inpatient care and less than 20% – on outpatient care. It has been established that 73% of costs are associated with 10% of patients with severe disease. The highest economic losses are brought about by treatment of COPD exacerbations. In Russia, the economic burden of COPD taking into account indirect expenses, including absenteeism (absence from work) and presenteeism (less effective work caused by illness), amounts to 24.1 bln. roubles. [2]

